Synthesis of data from across all WPs and across sites will be conducted to provide insight into optimal configuration of MHDUs in relation to the wider crisis care pathway and to inform potential future upscale

and roll out of MHDUs nationally. Data synthesis will adopt a Critical Interpretive Synthesis approach, as has been widely applied to the synthesis of quantitative and qualitative evidence in systematic reviews⁷³ and the development of evidence based practice.^{74, 75} In this approach 'constructs' are derived from the various analyses (i.e. from descriptive analysis or hypothesis testing of quantitative data, and thematic analysis of qualitative data) and mapped onto an integrative grid that explores how those analyses interface. This process enables the development of 'synthesising arguments' – analytical narrative - that offer explanatory insight into findings and inform applied learning from the research (here on MDHUs and optimal pathway configuration). A second interpretive workshop involving members of the research team and LEAP will be held to ensure that service user views and experiences inform this process.

The approach to using typical qualitative pathway stories from which to construct alterative economic models, as described in WP6 above, is one such data synthesis approach. A further set of constructs will be specified, derived from WP2, WP3 and WP4 quantitative analyses, and from analysis of our WP5 qualitative data (for examples, see Table 1). These constructs will reflect our levels of enquiry and will specifically explore issues around (but not be limited to):

- the crisis care pathway, including policy changes (macro), pathway configuration (meso), and clinical decision-making and experience of barriers to/ facilitators of admission to MDHU (micro);
- 2. the MDHU environment, including accommodation and staff mix (meso), and experience of assessment and treatment (micro);
- 3. population and crisis care, including identification of frequent users and under-represented groups (meso), and experience of pathway and clinical decision-making (micro).

	Impact of MDHU on A&E	Unit environment	Frequent users of MHDU
WP2/WP3 Time series analysis/ Synthetic control study	No impact on 4 hour breach		Reduction in informal admissions for people with an acute admission in preceding 2 years
WP4 Cohort study analysis	Few referrals to MDHU from A&E (compared to other referral sources)	Extended LoS on MDHU (>24 hours) no impact on outcomes post-discharge	Fewer acute admissions and increased engagement with community services post admission to MDHU for subgroup with previous MDHU admission
WP5 Qualitative interviews	A&E staff report very few referrals to MDHU accepted MDHU staff report high numbers of 'high risk' referrals from CRHT	MDHU service users report high satisfaction with unit environment, including accommodation in units with recliners rather than beds, and positive therapeutic engagement with MDHU staff	Subsample of service users with previous MDHU admission report positive experience of assessment and signposting while on MDHU and increased access to community

Table 1. Examples of hypothetical constructs that might be tested by data synthesis.
			services post-discharge from MDHU
--	--	--	-----------------------------------

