1 BACKGROUND

With bed occupancy high, staff under pressure and resources constrained, the UK Accident and Emergency (A&E) system has been described as near breaking point.¹ Two-thirds of people attending A&E multiple times for any reason will have had previous contact with specialist mental health services or have previously been admitted to an acute hospital for a mental health condition,² with frequent attenders at greater risk of psychiatric inpatient admissions.³ In 2012/13 alone, over 4,000 people with a mental health condition had attended A&E on multiple occasions (over 60 times) in the five years before the admission.⁴ Bed occupancy in inpatient psychiatric facilities is well above recommended levels with 91% of wards operating above the recommended occupancy rate.⁵ A recent study found that people presenting with a mental health issue were over 6 times more likely than people presenting with a physical concern to breach the four hour A&E wait time.² In response, a number of mental health decision units (MHDUs) have recently been developed across England.⁶⁻⁸ MHDUs provide dedicated 24-hour facilities for an enhanced mental health assessment and offer short-term support targeting people experiencing acute and complex mental health crises, for whom inpatient admission is being considered (differing in function from the triage wards found in some Mental Health Trusts that admit all people requiring inpatient care for purposes of assessment for ongoing care).⁹ The intention of MDHUs is to reduce the reliance on admissions to acute inpatient care, divert mental health service users from A&E and ensure parity of esteem for service users receiving expert and detailed assessments (see detailed specification in *Setting* below).^{7, 10} While recent single site studies in the USA and Australia, and preliminary local evaluations in the UK suggest that MHDUs have potential to reduce demand on A&E services and psychiatric inpatient care,^{6, 8, 11, 12} a rigorous, comprehensive study is needed to ascertain the structure and activities of operational MHDUs in England and provide an evidence base for their effectiveness and value for money.

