Study sites will be Mental Health NHS Trusts with MHDU, defined broadly as a hospital-based unit that receives targeted referrals of people in acute mental health crisis, prior to a decision about admission being made, for purposes of assessment, therapeutic input, and either subsequent admission, discharge or forward signposting to appropriate recovery and preventative services. To maximize generalisability, MHDUs in four contrasting Mental Health NHS Trusts will be evaluated in depth; South West London & St George's, Lincolnshire, Sheffield and Birmingham.

Sites have been chosen for reasons of a) feasibility; we have the support of host NHS Trusts to access participants and data, and b) there is an appropriate level of variation (as identified in the WP1 mapping exercise) in configuration of the MHDU model across the four sites to allow comparison and ascertain models of MHDU which are likely to be optimal with respect to service productivity, quality of care as experienced by service users and cost-benefit.

Primary and secondary outcome measures

ITS will be used to identify any effects observed across the four participating MHDUs on a range of outcome measures focussed on the activities of the relevant acute and mental health Trusts. The primary outcome measures (for mental health Trust and A&E department – acute Trust – respectively) are changes in the number and pattern of:

- informal admissions to mental health Trust adult inpatient wards
- A&E psychiatric presentations

The secondary outcomes are changes in:

Mental health Trust

- total inpatient admissions
- number of 0-5 day inpatient admissions
- average length of inpatient stay (bed days)
- compulsory admissions
- occupied bed days (daily mean for the week)
- out of area admissions (from the site MH Trust to other MH Trust or private provider)
- number of psychiatric liaison episodes in A&E
- transfer to MDHU by ambulance and police

Acute Trust (collected for each hospital which refers to the site MDHU)

- number of 4 hour psychiatric A&E breaches
- average length of psychiatric A&E wait
- number of 12 hour trolley waits
- number of admissions to an acute bed
- arrival at A&E by ambulance and police

Data collection for ITS

Outcome data will be collated as weekly series for 24 months pre- and 24 months post-implementation of MHDUs, totalling 208 (weekly) time points. This is more than the 40 data points (20 pre- and 20 post-

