change) typically considered as adequate for valid ITS model analysis,⁴⁰ and provides sufficient power to detect medium effects where they exist. For example, to detect a time x slope interaction with medium effect size on an outcome, a sample of 208 time points has > 99% power (assuming one parameter tested and no more than five factors entered in model; calculated using G-Power, 'linear multiple regression: fixed model, r^2 increase' module).

The metrics used as dependent measures within the ITS modelling will include key parameters associated with acute and psychiatric hospital activity. Waiting time in Accident and Emergency departments (A&E), especially performance against the UK's 4-hour waiting time target has recently been reiterated a key metric used to assess mental health care in acute care hospitals.⁴¹ Similarly, psychiatric inpatient admission (and emergency re-admission) and length of stay (LoS) remain a key driver of NHS hospital costs, especially when care is staff-intensive as is the case in mental health.⁴²

Aggregated service use data over the relevant 208 weeks will be sourced locally from mental health Trusts and A&E departments (acute hospital Trusts) of participating MHDU sites, as detailed above, through contact with Information Management & Technology (IM&T) departments at each Trust. Contact will be made with IM&T departments in advance of the study beginning and test data downloads requested and fields validated. Where there is more than one A&E department referring to the MDHU in any one site we will aim to collect A&E data from each acute hospital Trust, and at least from the main general hospital in that area.

Analytical strategy for ITS

We will provide both visual representations of the results in the form of graphical representations of outcome data over time and tables of the parameter estimates from the regression analyses for statistical inference. Graphical analysis will help to identify any stepwise change in outcome measures as a result of the introduction of MHDUs as well as detect changes in activity patterns before and after the introduction of MHDUs.

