Formal statistical analysis will include a time series regression analysis, used to estimate the effectiveness of introducing MHDUs on outcome variables. We will adopt an autoregressive integrated moving average (ARIMA) modelling approach,⁴³ as it allows for accurate analysis of outcomes, taking into account any serial correlation, background variation and underlying trends independent of the intervention over time. ARIMA modelling has previously demonstrated successful prediction emergency department (ED) presentations and hospital admission,⁴⁴ including psychiatric visits.⁴⁵

Initially, for each outcome, to check for serial auto-correlation due to repeated measures, we will examine the plot of residuals from regression analyses and use the Durbin-Watson test. Where no significant autocorrelation is detected, we will use a simple time series regression model. If significant autocorrelation exists, then adjustment for autocorrelation will be made using the ARIMA method.

For each outcome, we will calculate regression coefficients corresponding to both change in level (outcome) and trend (slope) after the introduction of MHDUs. In this model, the estimated parameters of interest are as follows: 1 the underlying trend prior to MHDU introduction (b1); 2 the level change immediately following MHDU introduction (b2); 3 the slope change from pre- to post-MHDU introduction

(using the interaction between time and change; b3); 4 the trend (slope change) following MHDU introduction (b1_b3).

Secondary analyses will include separate time series analyses of informal admissions to mental health Trust adult inpatient wards administered considering only people with discharge from psychiatric inpatient services in the last 24 months. In a similar manner, separate analyses of A&E psychiatric presentations will be administered considering only people with a previous A&E visit in the last 24 months. This is to ensure that we can estimate the effect of introducing MDHU on those populations most likely to be repeat users of mental health inpatient care and A&E respectively. External validity will be explored by examination of primary outcomes in subgroups, including but not limited to gender and ethnicity.

Semi-structured interviews; Data collection and interpretation of time series analysis

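### The 4-hour A&E breach outcome is analysed only as a count, so it cannot separate fewer psychiatric presentations from better performance against the 4-hour target; the proportion breaching should be analysed beside it

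*Protocol*

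**What the plan says.** Protocol section 5, WP2, Primary and secondary outcome measures, names "A&E psychiatric presentations" as the primary outcome for the acute Trust. The acute-Trust secondary outcomes include "number of 4 hour psychiatric A&E breaches" and, on the next line, "average length of psychiatric A&E wait". WP3, Outcome measures, repeats the list, with secondary outcomes conditional on access to the national datasets. Section 7.3.2 also describes the breach measure as a number.

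The analytical strategy for the WP2 time series states: "For each outcome, we will calculate regression coefficients corresponding to both change in level (outcome) and trend (slope) after the introduction of MHDUs". It names no denominator, offset or adjustment for the number of presentations. The WP2 data are weekly, "totalling 208 (weekly) time points"; the WP3 data are monthly.

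The rationale for the waiting-time measures, in WP2, Data collection for ITS, refers to A&E waiting time, "especially performance against the UK's 4-hour waiting time target has recently been reiterated a key metric used to assess mental health care". Section 1 says that the units are intended, among other aims, to "divert mental health service users from A&E". Research question 3a in section 4 asks about the effect on A&E psychiatric episodes and breaches.

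**The concern.** A breach count is the number of presentations multiplied by the proportion of them that breach. The intervention is designed to change the first factor, which is itself a primary outcome. Performance against a waiting-time target, the reason given for measuring waits, concerns the second factor. A model of the count alone returns one number for both.

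Two misreadings follow. A fall in the count may be taken as shorter waits when only volume fell. A flat count may be taken as no effect when volume fell and the proportion breaching rose. The second would reach the study's conclusions: Table 1, in the data synthesis section, gives a null result on the 4-hour breach from WP2/WP3 as a hypothetical example of a construct on A&E impact.

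**Working it through.** **The Protocol's own figure.** WP2 claims more than 99% power for a medium effect with 208 weekly points, one tested parameter and at most five factors. I assumed the conventional medium effect f² = 0.15 and two-sided 5% (the level stated for WP4). The noncentrality is then 0.15 × 208 = 31.2, and the power is 0.9998 with five predictors. The claim reproduces. It is not in dispute and does not bear on what the count measures.

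**Inputs the documents do not give.** Weekly psychiatric presentations (n) and the proportion breaching (p). I assumed n = 30, 50 or 100 and p = 20% or 40% for the simulation, and single illustrative values for the arithmetic.

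**Identity.** Expected breaches = n × p. If n changes by a fraction a and p by a fraction b, the count changes by (1 + a)(1 + b) − 1.

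- *Volume only (b = 0).* The count changes by exactly a. With n = 60 and p = 30%, 60 × 0.30 = 18. After a 10% fall in presentations, 54 × 0.30 = 16.2, a 10% fall at unchanged risk.
- *Offsetting changes.* With a = −20% and b = +25%, 0.80 × 1.25 − 1 = 0. For example, 100 × 0.20 = 20 and 80 × 0.25 = 20. The count is flat although the proportion has risen.
- *Case mix.* If six non-breaching presentations leave the 60, the count stays at 18 and the proportion becomes 18/54 = 33.3%, up from 30.0%, although the same 18 people breach.

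**Simulation.** Each series had 104 weeks before and 104 after, Poisson presentations, binomial breaches at constant p and no autocorrelation. Segmented linear regression tested the level change at 5%, with 1,000 runs per setting. Entries are the percentage of runs with a significant level change, for falls in presentations of 0% / 10% / 20%.

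| n per week | p | Count | Proportion |
|---|---|---|---|
| 30 | 20% | 5.3 / 13.7 / 45.9 | 4.8 / 4.5 / 4.5 |
| 30 | 40% | 4.4 / 25.4 / 74.2 | 5.5 / 4.6 / 4.6 |
| 50 | 20% | 4.3 / 19.9 / 67.7 | 4.6 / 5.0 / 5.4 |
| 50 | 40% | 4.6 / 39.2 / 93.2 | 4.6 / 4.8 / 4.0 |
| 100 | 20% | 3.9 / 38.6 / 92.2 | 4.9 / 4.6 / 4.7 |
| 100 | 40% | 5.2 / 64.0 / 99.9 | 4.3 / 5.6 / 4.7 |

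Simulation error around 5% is about ±1.96 × √(0.05 × 0.95/1000) = ±1.4 percentage points, so the proportion analysis holds its nominal level throughout. The count rejections are not false positives for the count, which really did fall. They would be false only if read as a change in the risk of breaching.

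**The case against.** The strongest reply is that the outcomes should be read as a set. The average psychiatric A&E wait sits beside the breach count, is modelled in the same way and does not scale with volume. A pure volume effect would lower the count and leave the average unchanged, which would warn a careful reader. This stands in part. The average does address timeliness, but it can stay still while the share beyond four hours moves, and the reverse.

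Second, WP2 is framed around the activity of the Trusts. Fewer breaches because people go elsewhere is an intended effect, and the count measures it properly. This stands, and it is why the count should remain an analysed outcome.

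Third, a proportion is not clean either. Its denominator is an outcome of the intervention, and the case-mix example above shows it rising when nobody waits longer. This also stands: neither measure is enough alone.

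A reader might go further and infer that the count is the wrong outcome and must be replaced, that timeliness is unmeasured, or that the breach result is likely to have the wrong sign. The documents do not support these readings. The 4-hour target is cited as a key metric for assessing care, not defined as this study's endpoint. The average wait is analysed. The wrong-sign case needs the units to draw off quick, non-breaching attenders, whereas section 6 describes them as an alternative for people with excessive emergency-department stays; removing likely breachers would tend to lower both count and proportion.

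Finally, this is one of 13 secondary outcomes (8 mental health Trust, 5 acute Trust), so the primary outcomes are untouched.

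**Conclusion.** The point holds as a gap in the set of breach measures. Analysed only as a count, breaches change one-for-one with presentations at constant risk, and offsetting changes in volume and risk leave the count flat. The plan therefore has no analysed measure of performance against the threshold that it uses to justify measuring waits. A reader could form the ratio from the two reported series, but no level or slope change would be estimated for it.

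The direction follows from the identity and needs no assumption about volumes. The size does: the 46% to 99.9% (20% fall) and 14% to 64% (10% fall) rest on assumed weekly volumes and breach proportions, independent weeks and a simple linear model, and are illustrative only. An analysis plan not shown here might derive a rate, but the Protocol itself fixes the outcome as a number in both work packages.

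**What to change.** - **Outcome lists, WP2 and WP3 (section 5).** Keep the breach count as an analysed activity outcome. Add the proportion of psychiatric A&E presentations that exceed four hours, with numerator and denominator from the same hospitals and periods.
- **WP2 analysis.** Apply the existing segmented regression/ARIMA strategy to the weekly proportion, or use a count model with log presentations as offset and an explicit way of handling autocorrelation.
- **WP3 analysis.** Use the monthly proportion where the national data allow it.
- **Interpretation.** Report count, proportion and presentations together. Base statements about the 4-hour target, including any carried into the data synthesis, on the proportion, and note that diversion may change the case mix of those who still attend.

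Cost: one additional secondary analysis in each work package and a case-mix caveat. No new data are needed, because presentations are already a primary outcome in both. The offset model would be a second model type alongside the planned one; analysing the weekly proportion avoids that.

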Semi-structured interviews (n=5 per site) will be held with strategic managers in each site, including MHDU manager, Acute Care Pathway lead, mental health lead commissioner (or their equivalent locally) and the A&E manager and A&E clinical director at the main general hospital at each site. Interviews will seek to identify any changes to the crisis care pathway within the duration of the time series, including the introduction or withdrawal of services or new initiatives, either as a result of national policy changes or reflecting local commissioning or clinical decision making priorities, including provision of services outside of the NHS Mental Health Trust (e.g. by third sector agencies) and changes in policy or protocol relating to the assessment and managing of psychiatric presentation to A&E. These interviews will be conducted by the Post-Doctoral Researcher to reflect the strategic level of interviews.

Alongside documented acute and crisis care pathway maps, interviews will seek to identify all aspects of the crisis care pathway, both directly provided by the mental health Trust and by other agencies, their referral routes (to acute admission and to the MHDU), and the assumed impact of these services on outcomes of interest to the study (including seasonal impacts). Where possible, internal reports and evaluations will be used to triangulate interviews, with quality of evaluation methods taken into consideration when interpreting findings. Changes in pathway or withdrawal of services or introduction of new initiatives that coincide with the time series – both prior to and following the interruption point – will be of particular interest and will be carefully dated in relation to the time series. This might include reconfiguration of services not directly related to crisis care – e.g. community mental health teams – that might nonetheless impact on our outcomes of interest.

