Interviews will be used to build a comprehensive, descriptive model of the crisis care pathway (including changes to the pathway) – rather than subject to a phenomenological analysis – and the known and assumed impact on our outcomes at all points along the 48 month time series in each site carefully mapped. To account for potential confounding of any identified service reconfiguration or changes to models of care, sensitivity analysis comparing the months following the introduction of MHDUs to the same period prior to the service change will be administered. These data will be used in interpreting time series curves for each of our outcomes (for example, where reconfiguration of community services was followed by a temporary spike in inpatient admissions, or where the introduction of a street triage service coincided with a sustained reduction in A&E presentation). Acute

care and crisis pathway maps will also be used to inform development of service user pathways developed in WP5.

WP3: Synthetic control study (months 1-18)

Objective

 Administer a synthetically controlled time series analysis, using routinely collected mental health Trust and Emergency Department data to assess whether the introduction of MHDUs in four sites effects psychiatric inpatient admissions and A&E psychiatric episodes.

Outcome

• An estimate of the extent to which change in key service parameters (i.e., informal psychiatric admissions and mental health presentations at ED) in the pre- and post-interruption period are explained by the introduction of MHDUs.

Design and Methods

The inclusion of comparative control sites or unit in interrupted time series, in which no change occurs, improves the specificity of the evaluation and better controls for secular trends over the baseline, change or intervention, and follow-up periods.³⁷ Advanced synthetic control methods will be used for controlled analysis to estimate a robust counterfactual against which to compare the impact of the introduction of each of the four participating MHDUs on primary outcome variables.

Site selection

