We will use Generalized Linear Modelling (GLM) to develop Logistic and Poisson regression models which examine relationships between important service/service user characteristics and (individual) mental health service use data post discharge from the MHDU. For example, Poisson regression will be employed to estimate relative risks (RRs) and 95% confidence intervals (CIs) for the associations of independent variables (ethnicity, diagnosis, previous inpatient admissions, accommodation status, comorbidity, previous health care utilisation, time spent in MHDU, severity of presentation as indicated by discharge destination after MHDU assessment)⁵⁸ with those outcome measures that use count data (e.g., total number of admissions and numbers of A&E presentations in the 9 months after MHDU discharge). We will also develop regression models using GLM (e.g., Linear and/or Logistic, depending on data distribution) to explore which independent variables are most closely related to change in primary outcome variables (e.g., decrease in number of A&E presentations from the period pre-MHDU admission to the period post-MHDU discharge). For all categorical independent variables in models (e.g., diagnosis), the reference group will be selected on the basis of it being 1) the largest or 2) most interpretable.⁵⁶ To account for missing data on relevant variables (e.g., accommodation status), a multiple imputation approach will be adopted to create imputed datasets using chained equations.⁶⁶ We will check for the occurrence of multicollinearity and calculate Cook's distances⁶⁷ to identify influential outliers. We will use two-sided significance tests for all analyses with statistical significance set at a p value of 0.05.

WP5.Qualitative longitudinal study (months 7-21)

Objective

• To examine qualitative interview data to understand experiences before, during, and after referral to MHDU from the perspective of service users and carers, and the decision-making process of A&E, crisis services and MHDU staff along the crisis care pathway.

Outcomes

- A detailed understanding of MHDU service user and carer experience including pathways before and after MHDU admission.
- A detailed understanding of staff experience of MHDU implementation, particularly that concerning decisions made about MHDU referral/admissions, assessments and onward signposting.

Design and Methods

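### WP2 names no seasonal term in either branch of its time series rule and does not model dated service changes, so both can be mistaken for an MHDU level change

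*Protocol*

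**What the plan says.** All of this is in Protocol section 5, WP2.

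- **Data** (the ITS data collection paragraph): "Outcome data will be collated as weekly series for 24 months pre- and 24 months post-implementation of MHDUs, totalling 208 (weekly) time points".
- **Claim** (Design and Methods): the design is said to permit control of baseline variation, periodicity and cyclical trend before change effects are examined.
- **Decision rule** (Analytical strategy for ITS): residuals are plotted and the Durbin-Watson test applied. "Where no significant autocorrelation is detected, we will use a simple time series regression model"; if autocorrelation is significant, ARIMA is used to adjust for it.
- **Estimates** (same heading): for each outcome, "we will calculate regression coefficients corresponding to both change in level (outcome) and trend (slope) after the introduction of MHDUs". The parameters of interest are the pre-trend b1, the level change b2, the slope change b3 and the post-opening trend.
- **Season** (Semi-structured interviews): managers are asked about crisis services and "the assumed impact of these services on outcomes of interest to the study (including seasonal impacts").
- **Service changes** (same heading): these are to be dated against the series and used to interpret the curves. For confounding, a "sensitivity analysis comparing the months following the introduction of MHDUs to the same period prior to the service change will be administered".

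Only the protocol is at hand; a statistical analysis plan may exist.

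**The concern.** The protocol expects seasonal effects and claims that the design can handle cycles, yet the rule it writes out has no step that puts season into the model. Its only formal trigger for anything beyond a simple regression is Durbin-Watson, a lag-1 statistic. Either way the named response is none, or an adjustment for autocorrelation. A fixed annual cycle is part of the mean of the series, so correcting the error structure does not by itself take it out of b2.

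The service changes raise the same difficulty. A change close to the opening looks like a level change at the opening. The interviews will supply its date, but the date is used only for interpretation and one comparison.

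At stake is b2 for the two primary outcomes, informal admissions and A&E psychiatric presentations, at each site.

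**Working it through.** **Inputs.** From the Protocol: 208 weekly points, taken as 104 before and 104 after opening; a model with intercept, time, step and time-by-step; two-sided 5% ("We will use two-sided significance tests for all analyses with statistical significance set at a p value of 0.05", stated under WP4 for all analyses). Assumed, because the Protocol gives no figures: the amplitude A of the annual cycle (half of peak to trough, 0 to 1.0 residual SD), independent normal errors, and a service-change step of 0.5 SD.

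**1. The plan's own figure.** The plan states that "a sample of 208 time points has > 99% power (assuming one parameter tested and no more than five factors entered in model"), and this is "to detect a time x slope interaction with medium effect size on an outcome". Taking medium as f² = 0.15, the noncentrality is 0.15 × 208 = 31.2 on 1 and 202 degrees of freedom. Power is 0.9998, so the stated figure reproduces. It concerns the slope change, not b2.

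**2. Seasonal bias.** Project a 52-week sinusoid by least squares on the four model terms and vary the opening date through the year.
- Bias in b2: maximum 0.956A, mean absolute value 0.956A × 2/π = 0.61A, zero at the most favourable date.
- Bias in b3: zero, because each segment holds two whole cycles.
- Standard error of b2: 0.277 SD (close to √(8/104) = 0.277).

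At A = 0.4 SD the largest bias is 0.956 × 0.4 = 0.38 SD, or 0.38/0.277 = 1.4 standard errors. For scale, a Poisson-like series averaging 20 a week (assumed) has SD √20 = 4.47, so A = 0.4 × 4.47 = 1.79 a week, about 9% of the mean.

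**3. What Durbin-Watson does** (one-sided 5%, simulated cut-off 1.80, no MHDU effect; worst opening date / random opening date).

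| A (SD) | Flagged by Durbin-Watson | False-positive b2 among series that pass |
|---|---|---|
| 0 | 5% / 5% | 5% / 5% |
| 0.3 | 14% / 15% | 16% / 11% |
| 0.4 | 25% / 27% | 26% / 15% |
| 0.5 | 41% / 46% | 37% / 21% |
| 0.8 | 92% / 94% | 71% / 44% (few series pass) |
| 1.0 | 99.6% / 99.8% | almost none pass |

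Repeat simulations at A = 0.4 put the last column at 15-27%.

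**4. If the series is flagged.** The ARIMA order is not stated. Non-seasonal AR(1) errors were tried as one possible choice, at the worst date. The mean false b2 is 0.29 SD at A = 0.3, 0.49 SD at A = 0.5 and 0.91 SD at A = 1.0, and b2 is significant in 17%, 33% and 57% of series. Detection alone therefore does not cure the bias.

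**5. With one annual sine/cosine pair.** False-positive b2 is about 5% at every amplitude under ordinary regression and 5-8% with AR(1) errors (600 runs each). The standard error of b2 rises from 0.277 to 0.295 SD, a factor of 1.065. Power for b3 with seven predictors remains 0.9998.

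**6. Service change.** A step of 0.5 SD with no MHDU effect:

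| Weeks from opening | Share passed into b2 | False-positive b2 | Flagged by Durbin-Watson |
|---|---|---|---|
| +4 | 85% | 34% | 5% |
| +8 | 71% | 24% | 6% |
| +12 | 58% | 18% | 7% |
| ±26 | 18-19% | 6% | 7% |

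Adding a step term at the known date returns the rate to about 5% (4.5-5.2%).

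**7. The planned comparison.** If the reference period is the 13 or 26 weeks just before opening, season can bias the contrast by up to 1.27A. If it is the same calendar months a year earlier, seasonal bias is zero. Neither reading by itself separates a service change near the opening from the MHDU.

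**The case against.** The case on the other side has five parts.

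- **Durbin-Watson is not blind to season.** A reader might infer that a lag-1 test cannot detect a 52-week cycle. That is not so: a smooth annual cycle has lag-1 correlation 0.99, and the test flags over 90% of series at 0.8 SD. The residual plot is a second look. This stands; the gap is for small to moderate cycles, and in what follows a flag.
- **Silence is not exclusion.** The listed quantities are parameters of interest, not necessarily every model term. The power statement allows up to five predictors, of which time, step and interaction take three, leaving room for a harmonic pair. ARIMA could carry seasonal orders, and an analysis plan may say so. This is fair. But the protocol goes beyond leaving detail open: it writes out the trigger and both branches, and the simple-regression branch as written has no seasonal term.
- **The slope matters more.** The powered effect is the slope change, and WP6 draws on sustained trend changes. This stands in part: season does not bias b3. But b2 is listed for every outcome and not ranked below b3.
- **The sensitivity analysis may be sound.** It is tempting to read it as a plain before/after comparison without trend. The sentence does not say that; it is ambiguous.
- **WP3 is a safeguard.** The synthetic control study covers the same primary outcomes and can absorb season and national shocks shared with control sites. It cannot absorb a change confined to one site's pathway.

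**Conclusion.** The point holds as one that should be fixed. Followed as written, the WP2 rule can report part of an annual cycle, or of a nearby local service change, as an MHDU level change. The seasonal bias is up to 0.96A in b2, with mean 0.61A and none in b3; this follows from the 104+104 week design alone. The error rates rest on assumed amplitudes and step sizes, independent errors and, for the flagged branch, a non-seasonal AR(1) choice that the protocol does not specify. They show what could happen, not what will.

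The documents do not support the stronger conclusions that the WP2 analysis is invalid, that season is ruled out of the model, or that the effect estimates as a whole are unprotected.

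**What to change.** 1. In Analytical strategy for ITS, include annual harmonic terms (one sine/cosine pair) or month terms, or seasonal ARIMA terms, in both branches by default.
2. Check the residual autocorrelation function to lag 52 in addition to Durbin-Watson.
3. In the Semi-structured interviews text, add a step term at each interview-dated service change to the same segmented model, and report b2 and b3 with and without these terms.
4. If the before/after comparison is kept, define which period is compared with which.

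This is a wording change and needs no new data. The harmonic pair widens the standard error of b2 by about 7% and leaves the stated power for the slope change at 0.9998. Intervals will be wider where a service change falls close to the opening; there the data hold little information to tell the two apart.
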